8.5 Analysis of baseline characteristics

The demographic characteristics of enrolled participants will be compared by study group.

8.6 Analysis of immunogenicity

The serum anti-CS antibody titre and avidity responses for each treatment arm will be compared to the titre before vaccine administration as follows:

For group 1 to 6:

- Number (%) in each study group with >4-fold rise in titre from baseline to:
 - One month after first dose
 - One month after second dose
 - One month after the third dose
 - Six months after the first dose
- The geometric mean-fold rise in each study group from baseline to:
 - One month after first dose
 - One month after second dose
 - One month after the third dose
 - Six months after the first dose.

For group 7:

- Number (%) in study group with >4-fold rise in titre from baseline to:
 - One month after first dose
 - Two months after first dose
 - One month after the second dose
 - Six months after the first dose
- The geometric mean-fold rise in study group from baseline to:
 - One month after first dose
 - Two months after first dose
 - One month after the second dose
 - Six months after the first dose.

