3 OBJECTIVES

The trial has the following objectives:

- To assess the safety and immunogenicity of the **standard formulation** of the RTS,S vaccine (RTS,S/AS01E) in Thai adults (Group 3 alone).
- To assess the safety and immunogenicity of the **adult** formulation of the RTS,S vaccine (RTS,S/AS01B) in Thai adults (Group 1 alone).
- To compare the safety and immunogenicity of a fractional dose RTS,S regime (where the third dose is a 1/5th of the standard dose) using the **adult formulation** (RTS,S/AS01B) to the safety and immunogenicity of fractional dose RTS,S regimes using either single or double doses of the standard formulation (RTS,S/AS01E), in Thai adults (Group 1 vs Group 2 and Group 1 vs Group 5).
- To compare the safety and immunogenicity of fractional dose regime (where the third dose is a 1/5th of the standard dose) using a single dose of the **standard formulation** (RTS,S/AS01E) to the safety and immunogenicity of fractional dose RTS,S regime using a double dose of the standard formulation (RTS,S/AS01E), in Thai adults (Group 2 vs Group 5).
- To compare the serologic response to RTS,S/AS01E vaccine when co-administered with DHA-PIP + SLD-PQ with RTS,S/AS01E vaccine alone in adults, when RTS,S/AS01E is given in either a fractional dose regime (where the third dose is a 1/5th of the standard dose) or a full standard dose regime (Group 3 vs. Group 4 and Group 5 vs Group 6).
- To compare the serologic response to RTS,S/AS01E vaccine co-administered with DHA-PIP + SLD-PQ, when RTS,S/AS01E is given in a fractional two-dose regimen (Month 0, standard dose and Month 2, fractional (1/5th) dose) with RTS,S/AS01E vaccine co-administered with DHA-PIP + SLD-PQ, when RTS,S/AS01E is given in a fractional three-dose regimen (Month 0 and Month 1, standard doses and Month 2, fractional (1/5th) dose) (Group 6 vs Group 7)

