4.2 Primary Outcome Measures

The primary outcome measures will be:

- The safety of the investigational vaccine in each group:
 - Occurrence of serious adverse events (SAEs) from the date of the first vaccination to 29 days after the last vaccination, according to the MedRA classification.
 - Occurrence of SAEs during the whole study period, i.e. during a 6 month follow up period from the receipt of first vaccination, according to the MedRA classification.

- For groups 1 to 6, the concentration of antibodies against *Plasmodium falciparum* circumsporozoite (anti-CS antibody), one month after the first dose (at Study month 1), one month after the second dose (at Study month 2), one month after the third dose (at Study Month 3) and six months after the first dose (at Study Month 6).
- For group 7, the concentration of antibodies against *Plasmodium falciparum* circumsporozoite (anti-CS antibody), one month after the first dose (at Study month 1), two months after the first dose (at Study month 2), one month after the second dose (at Study month 3), and six months after the first dose (at Study Month 6).

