8.2 The Number of Participants

The sample size calculations are based on the objective of comparing the serologic response to RTS,S/AS01E vaccine co-administered with DHA-PIP + SLD-PQ with RTS,S/AS01E or RTS,S/AS01B vaccine alone in adults. This is a phase II trial. Sample sizes for phase II trials are usually small, as safety is still of paramount importance. Valid sample sizes for comparing sample sizes between two groups are usually obtained using exact test methods such as the Fisher's exact test power calculations. This is done using simulations as sample size formulas are not well developed. To estimate the sample size we use a four-fold increase in anti-CS antibody titre as an assumed correlate of protection. For the sample size calculation, we assume that the background rate of response in the reference groups will be 5% and the true rate of anti-CS antibody response in the vaccine groups is 80%. We wish to exclude, for the vaccine, a one-tailed lower 95% CI for the reference-vaccine group difference of lower than 30%. The study aims to detect this difference with 90% power (because the detectable difference is big) and testing at 5% significance level. With these assumptions, and using the method of Blackwelder[37] for precision-based sample size calculations, a total of 20 participants per group would be needed for arms 1 and 2 because the anticipated difference is too big. However, for arms 3 to 7 (Table 3 below), we will need more participants per group because a smaller detectable effect is anticipated. Using the Fisher's exact test power simulations, a difference in serologic response of 30% (say 65% vs 95%) gives approximately 80% power with a sample size of 30 participants in each group testing at 5% significance level. Therefore the total sample size for all the 7 arms will be 190 participants.

The size of study groups is relatively small hence it is imperative to minimise potential losses. Whenever possible an attempt will be made to replace study participants should a participant be withdrawn or choose to withdraw. The stata command for obtaining the Fishers exact test power simulations is: `power two proportions 0.65 0.95, test(fisher) n1(30) n2(30)`. This has been performed in Stata 14.

The required sample sizes are summarized as follows:

Table 3: Sample size and vaccine vials required for each arm

Group	# participants	Vaccine	Dose M0	Dose M1	Dose M2	Antimalarial	vaccine vials required

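### Section 8.6 compares each arm only with its own baseline; no between-arm analysis of anti-CS concentration is stated, although Objectives 3 to 6 are between-arm

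*Protocol*

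**What the plan says.** Section 4.2 makes anti-CS concentration the primary immunogenicity outcome: "For groups 1 to 6, the concentration of antibodies against" the circumsporozoite protein, measured at Months 1, 2, 3 and 6, with a parallel entry for Group 7 at the same months.

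Section 3 has six objectives. The first two describe one arm each. The other four compare arms. Objective 3 names "Group 1 vs Group 2 and Group 1 vs Group 5", Objective 4 names 2 v 5, Objective 5 is "To compare the serologic response to RTS,S/AS01E vaccine when co-administered with DHA-PIP + SLD-PQ with RTS,S/AS01E vaccine alone in adults" (3 v 4 and 5 v 6), and Objective 6 names 6 v 7. The summary closing Section 2 lists two major aims. The first is to confirm that co-administered antimalarials do not lower the vaccine's immunogenicity.

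Section 8.6 states one comparison: "The serum anti-CS antibody titre and avidity responses for each treatment arm will be compared to the titre before vaccine administration". Two summaries follow at each time point: "Number (%) in each study group with >4-fold rise in titre from baseline to" and "The geometric mean-fold rise in each study group from baseline to". It names no pair of arms, no between-arm effect measure and no between-arm test.

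Section 8.2 sizes the trial on "a four-fold increase in anti-CS antibody titre as an assumed correlate of protection". For arms 3 to 7 it uses Fisher's exact test on 65% v 95% responders with 30 per arm, and gives about 80% power. Section 8.4 says that the per-protocol analysis will compare participants by the agent received, without naming a variable or a method.

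**The concern.** Every arm receives RTS,S, so every arm should show a rise from baseline. Two arms can both rise strongly and still differ from each other, so the comparison in Section 8.6 cannot answer Objectives 3 to 6.

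This is more than detail left for a statistical analysis plan. Section 8.6 does state a comparison, and it is not the one that four of the six objectives need. An analysis plan that followed 8.6 would inherit the gap. One that departed from it would be choosing the main between-arm comparison outside the protocol, in an open-label trial.

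The question most exposed is the antimalarial one. If the only worked-out between-arm method is a test on responders, and most vaccinees respond, a real fall in titre could go undetected and be read as no reduction.

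**Working it through.** **Inputs from the protocol (8.2, 4.8.4):** 65% v 95% responders; 30 per arm in Groups 3 to 7 and 20 in Groups 1 and 2; 5% level; Fisher's exact test. Response rates mentioned in 8.2 include 80% and 95%.

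**Assumptions not in the protocol:** log10 titre is about normal with equal SD in the two arms; baseline variation is small, so that log titre and log fold rise have nearly the same SD; that SD is 0.4, with a range of 0.3 to 0.5.

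**1. The plan's own figure.** Summing both binomial distributions over all tables with two-sided Fisher p ≤ 0.05, at 65% v 95% and 30 v 30, gives 78.8% power. The stated figure of about 80% reproduces.

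**2. The planning pair as a shift.** Shift = z(0.95) − z(0.65) = 1.645 − 0.385 = 1.26 SD. A two-sample t-test on log titre has noncentrality 1.26/√(1/30 + 1/30) = 4.88 on 58 df, which gives 99.8% power against 78.8% for the responder test.

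**3. The shift a t-test can detect.** At 30 v 30 and two-sided 5%, 80% power is reached at 0.736 SD. In fold terms, 10^(0.736 × SD) is 1.7 at SD 0.3, 2.0 at 0.4 and 2.3 at 0.5. The planning pair, 10^(1.26 × SD), is 2.4, 3.2 and 4.3.

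**4. The same fall seen through the responder rate.** New rate = Φ(z(p) − 0.736).

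| Starting rate | Rate after the fall | Fisher power, 30 v 30 | t-test power |
|---|---|---|---|
| 80% | Φ(0.842 − 0.736) = 54% | 47% | 80% |
| 95% | Φ(1.645 − 0.736) = 82% | 18% | 80% |

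**5. The ceiling.** If one arm has 30 of 30 responders, 5 non-responders of 30 in the other give p = 0.052 and 6 give p = 0.024. At least 6 of 30 must therefore fail to respond before the test rejects.

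**6. All Section 3 contrasts on the log scale.** Geometric mean ratio detectable with 80% power, two-sided 5%, existing numbers, no baseline adjustment:

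| Contrast | n | SD 0.3 | SD 0.4 | SD 0.5 |
|---|---|---|---|---|
| 3 v 4, 5 v 6, 6 v 7 | 30 v 30 | 1.66 | 1.97 | 2.33 |
| 1 v 5, 2 v 5 | 20 v 30 | 1.77 | 2.14 | 2.59 |
| 1 v 2 | 20 v 20 | 1.87 | 2.31 | 2.85 |

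**The case against.** **The responder rate is not the only measure.** A reader might infer that Objectives 3 to 6 rest wholly on the four-fold responder rate. Section 8.6 does not support that. It also lists the geometric mean-fold rise, a continuous log-scale summary, and comparing it between arms would recover much of the lost power, by an amount that depends on baseline variance. This stands. What rests on the responder rate is the sizing and the only between-arm test with a stated method.

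**Between-arm comparison is intended.** A reader might also infer that the protocol never means to compare arms. Section 3 names the pairs, 8.2 sizes for a comparison, and 8.4 speaks of comparing participants. The list in 8.6 can be read as defining response, by group, which is what Objectives 1 and 2 need. The model and covariates could reasonably sit in an analysis plan that is not shown. All this is fair, but none of it supplies a between-arm analysis of the primary variable, and the one comparison that 8.6 does state is within arm.

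**The loss of power is conditional.** At the planning pair the responder test has 79% power. Starting from 80% responders, it reaches 80% power at a fall of 1.03 SD, which is 2.6-fold at SD 0.4 against 2.0-fold on the log scale: a modest gap. Near-zero power appears only with almost universal response (0.4% from a 99% rate), and the protocol gives no such rate. The four-fold rise was also chosen as an assumed correlate of protection, which is a reason to keep reporting it.

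**Conclusion.** The point holds as a mismatch within the protocol: the stated immunogenicity comparison is with each arm's own baseline, while Objectives 3 to 6 and the lead aim need comparisons between arms on anti-CS concentration, and none is stated for that variable.

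The cost of relying on the one worked-out between-arm test depends on where response settles. For a fall that a log-scale t-test detects with 80% power, Fisher's test has 47% or 18%, starting from 80% or 95% responders. The power comparison assumes log-normality and equal SDs. Expressing the fall as about 2.0-fold (1.7 to 2.3) needs the assumed SD of 0.4 (0.3 to 0.5) as well. The mismatch itself needs no assumption.

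The documents do not show that the four-fold endpoint is generally insensitive, or that arms will go uncompared.

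**What to change.** In Section 8.6, for each Section 3 contrast (1 v 2, 1 v 5, 2 v 5, 3 v 4, 5 v 6, 6 v 7), state that anti-CS concentration will be compared as a between-arm geometric mean ratio with 95% CI, from a linear model of log concentration on arm, adjusted for log baseline.

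Report it at the primary time points. Section 4.2 lists Months 1, 2, 3 and 6 without ranking them, so the sponsor should name the main one, for example Month 3.

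For 3 v 4 and 5 v 6, either judge the CI against a pre-stated and justified non-inferiority margin, or present it as estimation without claiming that immunogenicity is not reduced. Without a margin, even a geometric mean ratio leaves a non-significant result open to being read as no reduction.

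Keep the four-fold responder rate and the within-arm fold rise as supporting summaries.

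The synopsis labels Objective 5 with other pairs (2 v 3 and 4 v 6). The pairs used here are those of Section 3, which fit the objective's wording, and the synopsis should be aligned.

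The cost is a rewording of 8.6 and the work of justifying a margin if non-inferiority is to be claimed. Samples, assays and participant numbers stay as they are; the numbers per arm may prove small for a tight margin, and that should be checked when the margin is set.

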9 DIRECT ACCESS TO SOURCE DATA/DOCUMENTS

Direct access to all trial related source data/documents will be granted to authorized representatives from the sponsor, PATH Malaria Vaccine Initiative, GSK, Research Ethics Committees (RECs), and the regulatory authorities to permit trial-related monitoring, audits and inspections.

10 QUALITY CONTROL AND QUALITY ASSURANCE PROCEDURES

The study will be conducted in accordance with the current approved protocol, ICH GCP, relevant regulations and standard operating procedures. Data will be evaluated for compliance with the protocol and accuracy in relation to source documents. Following written standard operating procedures, the monitors will verify that the clinical trial is conducted and data are generated, documented and reported in compliance with the protocol.

11 ETHICS

Ethical approval will be sought prior to commencing the study through the relevant Research Ethics Committees. Indemnity for the trial will be provided by the University of Oxford. SAEs will be reported to the medical monitor, DSMB, ethics committees and the Sponsor. GCP training will be provided to all staff/investigators who have no valid training certificate prior to commencing the studies.

11.1 Declaration of Helsinki

The Investigators at each site will ensure that this study is conducted in accordance with the principles of the Declaration of Helsinki.

11.2 ICH Guidelines for Good Clinical Practice

The trial will adhere to the Research Governance policies of the University of Oxford and the ICH GCP.

11.3 Approvals

The protocol, informed consent form, participant information sheet, and other written participant information / materials will be submitted to appropriate Research Ethics Committees (RECs), and regulatory authorities for written approval. The Principal Investigator will submit and, where necessary, obtain approval from the above parties for all amendments to the original approved documents.

11.4 Participant Confidentiality

The trial staff will ensure that the participants' anonymity is maintained. The participants will be identified only by participants ID number on the CRF and in any electronic databases. All documents will be stored securely and only accessible to trial staff and authorized personnel. Only the sponsor representative, investigators, the clinical monitor, authorized individuals from the PATH Malaria Vaccine Initiative, GSK, the ethical committee(s) and the regulatory authorities will have access to the records. Data will be anonymized as soon as it is practical to do so.

With subject's consent, subject's clinical data and results from blood analyses stored in our database may be shared with PATH Malaria Vaccine Initiative, GSK, other researchers to use in the future. However, the other researchers will not be given any information that could identify the subject.

12 DATA HANDLING AND RECORD KEEPING

All study data will be stored under lock and key. The investigators will maintain and retain appropriate medical and research records and essential documents for this trial in compliance with ICH E6 GCP and regulatory and institutional requirements for the protection of confidentiality of volunteers. Only authorized, trained study staff will have access to study records. The participants will be identified by a study specific participants ID number and/or code in any database. The participants' names and any other identifying details will NOT be included in any study data electronic file.

The principal Investigator will be responsible for data management and for delegating the receiving, entering, cleaning, querying, analysing and storing all data that accrues from the study. The study staff will enter the data into the volunteers' CRFs, which will be in a paper and/or electronic format. This includes safety data, laboratory data (both clinical and immunological) and outcome data. Data will be managed and stored in MACRO® database, a GCP-compliant electronic data capture system.

The investigators will permit authorized representatives of the sponsor, ethical committee(s), regulatory agencies, authorized individuals from PATH Malaria Vaccine Initiative, GSK and the monitors to examine (and when required by applicable law, to copy) clinical records for the purposes of quality assurance reviews, audits and evaluation of the study safety and progress.

13 INSURANCE

The University of Oxford has a specialist insurance policy in place: - Newline Underwriting Management Ltd, at Lloyd's of London – which would operate in the event of any Participant suffering harm as a result of their involvement in the research.

14 PUBLICATION POLICY

All Investigators will be involved in reviewing drafts of the manuscripts, abstracts, press releases and any other publications arising from the study. Authorship will be determined in accordance with the ICMJE guidelines and other contributors will be acknowledged.

15 APPENDIX A: SUMMARY OF STUDY ARMS AND PROCEDURES

Month	Group 1 (n=20) $R_B R_B r_B$	Group 2 (n=20) $2xR_E 2xR_E 2xr_E$	Group 3 (n=30) $R_E R_E R_E$	Group 4 (n=30) $R_E R_E R_E + \text{DHA-PIP} + \text{PQ}$	Group 5 (n=30) $R_E R_E r_E$	Group 6 (n=30) $R_E R_E r_E + \text{DHA-PIP} + \text{PQ}$	Group 7 (n=30) $R_E r_E + \text{DHA-PIP} + \text{PQ}$
0	RTS,S/AS01B Standard dose (0.5mL)	RTS,S/AS01E Double Standard dose (1.0mL)	RTS,S/AS01E Standard dose (0.5mL)	RTS,S/AS01E Standard dose (0.5mL) + DHA-PIP+PQ	RTS,S/AS01E Standard dose (0.5mL)	RTS,S/AS01E Standard dose (0.5mL) + DHA-PIP+PQ	RTS,S/AS01E Standard dose (0.5mL) + DHA-PIP+PQ
1	RTS,S/AS01B Standard dose (0.5mL)	RTS,S/AS01E Double Standard dose (1.0mL)	RTS,S/AS01E Standard dose (0.5mL)	RTS,S/AS01E Standard dose (0.5mL) + DHA-PIP+PQ	RTS,S/AS01E Standard dose (0.5mL)	RTS,S/AS01E Standard dose (0.5mL) + DHA-PIP+PQ	No intervention in M1
2	RTS,S/AS01B 1/5 Standard dose (0.1mL)	RTS,S/AS01E Double 1/5 Standard dose (0.2mL)	RTS,S/AS01E Standard dose (0.5mL)	RTS,S/AS01E Standard dose (0.5mL) + DHA-PIP+PQ	RTS,S/AS01E 1/5 Standard dose (0.1mL)	RTS,S/AS01E 1/5 Standard dose (0.1mL) + DHA-PIP+PQ	RTS,S/AS01E 1/5 Standard dose (0.1mL) + DHA-PIP+PQ

R_B = Standard dose RTS,S/AS01B: 50µg RTS,S + standard dose AS01B (0.5ml containing 50µg MPL + 50µg QS21)

R_E = Standard dose RTS,S/AS01E: 25µg RTS,S + standard dose AS01E (0.5ml containing 25µg MPL + 25µg QS21)

r_B = Fractional dose RTS,S/AS01B (1/5th dose): 10µg RTS,S + 1/5 standard dose AS01B (0.1ml containing 10µg MPL + 10µg QS21)

r_E = Fractional dose RTS,S/AS01E (1/5th dose): 2.5µg RTS,S + 1/5 standard dose AS01E (0.1ml containing 2.5µg MPL + 2.5µg QS21)

2x = Double dose of R_E (i.e. 1.0ml) or r_E (i.e. 0.2ml), as indicated.

DHA-PIP = Dihydroartemisinin/piperazine (for 3 days; day of vaccination and two subsequent days)

PQ = Primaquine (single low dose on day of vaccination)

Study procedures

Month	Scr	M0				M1				M2				M3	M6 ^a	
Day of month		0 ^f	1 ^b	2 ^b	7	0	1 ^b	2 ^b	7	0	1 ^b	2 ^b	7	0	0	
Informed Consent	x															
Inclusion / Exclusion criteria	x	x														
Vaccination		x				x*				x						
DHA/piperazine**		x	x ^b	x ^b		x*	x ^b	x ^b		x	x ^b	x ^b				
PQ single low dose primaquine**		x				x*				x						
History of fever, current axillary temperature***	x	x	x ^b	x ^b	x	x	x ^b	x ^b	x	x	x ^b	x ^b	x	x	x	
Full medical history, vital signs, physical examination	x	x				x				x						
Ask about any concomitant medication	x	x	x ^b	x ^b	x	x	x ^b	x ^b	x	x	x ^b	x ^b	x	x	x	
Assessment of any adverse event(s)		x	x ^b	x ^b	x	x	x ^b	x ^b	x	x	x ^b	x ^b	x	x	x	
Assess for any withdrawal criteria		x	x ^b	x ^b	x	x	x ^b	x ^b	x	x	x ^b	x ^b	x	x	x	
Blood sample (mL)	Parasite microscopy****					0.5				0.5					0.5	
	Haematology Hb, WBC, PLT	2	2		2				2				2	2		
	Biochemistry ALT, AST, CREA	3	3		3				3				3	3		
	HBsAg, HCV, HIV	1														
	Immunology panel ^c		10			10				10				10	10	
	Piperazine & Primaquine levels*****		1 ^g	1 ^e	1 ^d	1 ^d	1 ^d	1 ^e	1 ^d	1 ^d	1 ^d	1 ^e	1 ^d			
	Blood volume per visit (mL)	6	16	1	1	6	11.5	1	1	6	11.5	1	1	6	15	10.5
	Maximum cumulative blood volume (mL)															94.5
Electrocardiogram (ECG)	x															
Urine pregnancy test	x	x				X				x						

* Procedures are not applicable for study group 7

** Only for study groups 4, 6 and 7, where applicable

*** Axillary temperature will be record from D0-D7 after each vaccination

a) first day of M6

b) Visits on days 1 and 2 post-vaccination are only applicable for study groups 4, 6, and 7 in Months 0 and 2, and for study groups 4 and 6 in Month 1.

c) the immunology panel consists of six assays to be processed at WRAIR:

**** Parasite microscopy for purposes of indicating whether volunteer has been exposed, and not as an assessment of protection.
 
***** Piperaquine and Primaquine levels for group 4 and 6 only. Additional drug level assessment for Primaquine will be done if additional data are required.
	
 • Plasmodium falciparum. Circumsporozoite Protein. (NANP)6 Ab.IgG • Plasmodium falciparum. Circumsporozoite Protein. (NANP)6 Ab.IgG Avidity • Plasmodium falciparum. anti-C-Term Circumsporozoite Ab.IgG • Plasmodium falciparum. anti-C-Term Circumsporozoite Ab.IgG avidity • Plasmodium falciparum. Circumsporozoite Full length (N+C-Terminal) • P falciparum. anti-full length CSP Ab.IgG avidity 
d) Drug level only for Piperaquine
 
e) Drug level for Piperaquine and Primaquine
 
f) If interval between screening and M0D0 is 3 days or less, screening lab results (haematology, biochemistry, parasite microscopy, and urine pregnancy test) can be used for enrolment (M0D0)
 
g) Drug level for Piperaquine and/or Primaquine will be assessed if additional data are required

---	---

Summary of participant visits

Group	Number of visit	Visit timepoints														
		Scr	M0				M1				M2				M3	M6
			D0	D1	D2	D7	D0	D1	D2	D7	D0	D1	D2	D7	D0	D0
1	9	x	x			x	x			x	x			x	x	x
2	9	x	x			x	x			x	x			x	x	x
3	9	x	x			x	x			x	x			x	x	x
4	15	x	x	x	x	x	x	x	x	x	x	x	x	x	x	x
5	9	x	x			x	x			x	x			x	x	x
6	15	x	x	x	x	x	x	x	x	x	x	x	x	x	x	x
7	13	x	x	x	x	x	x			x	x	x	x	x	x	x

All the study procedure will be performed by research team including research doctor, research nurse and research physician at healthy volunteer unit at Faculty of Tropical Medicine, Mahidol University.

Intervals between study visits

Interval	Optimal length of interval	Allowed interval
Screening to Month 0 / Day 0 (1 st vaccination)	0 to 30 days	-
Month 0 / Day 0 (1 st vaccination) to Month 1 / Day 0 (2 nd vaccination)	28 days	+/- 7 days
Month 1 / Day 0 (2 nd vaccination) to Month 2 / Day 0 (3 rd vaccination)	28 days	+/- 7 days
Month 2 / Day 0 (3 rd vaccination) to Month 3 / Day 0	28 days	+/- 7 days
Month 3 / Day 0 to Month 6 / Day 0	84 days	+/- 14 days

